5.4.3 Toxicities Associated with Atezolizumab

Atezolizumab will be withheld until resolution (i.e., return to Grade 0-1) for the following event(s):

- Grade ≥ 2 pneumonitis
- Grade ≥ 3 symptomatic hepatic toxicities that do not resolve to Grade 2 within 48 hours or Grade ≥ 3 asymptomatic hepatic toxicities that do not resolve to Grade ≤ 1 within 3 weeks of onset with the following exceptions:
 - For patients with Grade 2 AST, ALT, alkaline phosphatase abnormality at baseline, an increase to $>8\times$ the upper limit of normal (ULN) that does not resolve to Grade 2 within 48 hours (if symptomatic) or Grade ≥ 3 asymptomatic hepatic toxicities that do not resolve to Grade ≤ 1 within 3 weeks of onset (if asymptomatic) will be considered a DLT.
- Grade ≥ 2 diarrhea or colitis
- Symptomatic hypothyroidism, hyperthyroidism, pan hypopituitarism, or any Grade ≥ 3 endocrine events
- Grade ≥ 3 ocular events
- Grade ≥ 3 dermatologic events
- Grade ≥ 2 neuropathy
- Grade ≥ 4 neutropenia (absolute neutrophil count [ANC] $<500/\mu\text{L}$) lasting ≥ 7 days, thrombocytopenia, anemia, or Grade ≥ 3 febrile neutropenia
- Grade ≥ 3 non-hematologic, non-hepatic organ toxicity, excluding the following:
 - Grade 3 immune related AE (irAE) that resolves to Grade ≤ 1 within 3 weeks of its onset (may include events that resolve after medical treatment, including immunosuppressant therapy)
 - Grade 3 nausea or vomiting that resolves to Grade ≤ 1 within 72 hours of appropriate supportive therapy
 - Grade ≥ 3 fatigue that resolves to Grade ≤ 2 within 7 days
 - Grade 3 arthralgia that can be adequately managed with supportive care or that resolves to Grade ≤ 2 within 7 days

- Grade 3 fever (in the absence of any clinically significant source of fever) that resolves to Grade ≤ 2 within 7 days with supportive care
- Grade ≥ 3 laboratory abnormality that is asymptomatic and deemed by the Investigator not to be clinically significant
- Grade 3 tumor flare defined as local pain, irritation, or rash localized at sites of known or suspected tumor
- Grade 3 infusion reaction that resolves within 6 hours to Grade ≤ 1

These reactions, along with any DLTs, will be reviewed by the DMC on a case-by-case basis and may be considered DLTs if they meet the criteria outlined above. Atezolizumab treatment can be resumed in patients whose adverse reactions recover to Grade 0-1.

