Appendix Table 6 Guidelines for Management of Atezolizumab-Associated Pulmonary Toxicity

Pulmonary Events/ Pneumonitis	Severity	Management
	Grade 1	
 • May continue atezolizumab with close monitoring • Re-evaluate on serial imaging • Consider pulmonary consultation
	Grade 2	
 • Withhold atezolizumab • Pulmonary and ID consultation with consideration for bronchoscopy/BAL • Start 60 mg prednisone or equivalent per day • When improves to Grade 0 or Grade 1, then taper steroids over ≥ 1 month • Atezolizumab may be resumed if the event improves to Grade 0 or 1 within 12 weeks and corticosteroids have been reduced to the equivalent of oral prednisone 10 mg daily or less. • Treat as Grades 3-4 if recurrent episode of pneumonitis
	Grade 3 and 4	
 • Permanently discontinue atezolizumab • Bronchoscopy/BAL is recommended • Start 60 mg prednisone or equivalent per day. • Taper steroids over ≥ 1 month once symptoms improve to Grade 0 or 1. • If not improving after 48 hours or worsening: add additional immunosuppression (e.g., infliximab, cyclophosphamide, IVIG, or mycophenolate mofetil) • Contact Medical Monitor if atezolizumab is discontinued

BAL=bronchoscopic alveolar lavage; ID=infectious diseases; IVIG=intravenous immunoglobulin

Hepatic Events

Immune-mediated hepatitis has been associated with the administration of atezolizumab. Eligible patients must have adequate liver function, as manifested by measurements of total bilirubin and hepatic transaminases, and liver function will be monitored throughout study treatment.

While in this study, patients who present with right upper-quadrant abdominal pain and/or unexplained nausea or vomiting should have liver function tests (LFTs) performed immediately and reviewed before administration of the next dose of study drug.

If LFTs increase, concurrent medications, viral hepatitis, and toxic or neoplastic etiologies should be considered and addressed, as appropriate. Imaging of the liver, gall bladder, and biliary tree should be performed to rule out neoplastic or other causes for increased LFTs. Anti-nuclear antibody, perinuclear anti-neutrophil cytoplasmic antibody, anti-liver kidney microsomal

antibodies, and anti-smooth muscle antibody tests should be performed if an autoimmune etiology is considered.

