Appendix Table 7 Management Guidelines for Hepatic Events

Hepatic events	Severity	Management
	Grade 1	
 • Continue therapy • Continue LFT monitoring
	Grade 2	
 • Monitor LFTs more frequently until return to baseline values • If persists $\geq 5-7$ days: withhold therapy and start 60 mg prednisone or equivalent per day; when LFTs are \leq Grade 1, taper steroids over ≥ 1 month, resume therapy if the event improves to Grade 0 or Grade 1 within 12 weeks and systemic steroid dose is ≤ 10mg oral prednisone equivalent per day
	Grade 3 and 4	
 • Discontinue therapy • Consider GI consult and liver biopsy to establish etiology of hepatic injury if necessary • Start 60 mg prednisone or equivalent per day • If LFT results do not decrease within 48 hours after initiation of systemic steroids, addition of an alternative immunosuppressive agent (e.g., mycophenolate or TNF-α antagonist) may be considered. • Taper steroids over ≥ 1 month, when symptoms improve to Grade 0 or 1 • Contact Medical Monitor if atezolizumab is discontinued

GI=gastrointestinal; LFT=liver function test; TNF- α =tumor necrosis factor alpha.

Gastrointestinal Events

Immune-mediated colitis has been associated with the administration of atezolizumab.

If the event is of significant duration or magnitude or is associated with signs of systemic inflammation or acute phase reactants (e.g., increased C-reactive protein, platelet count, or bandemia), the following are recommended:

- Perform sigmoidoscopy (or colonoscopy, if appropriate) with colonic biopsy with 3 to 5 specimens for standard paraffin block to check for inflammation and lymphocytic infiltrates for confirmation of the diagnosis of colitis. If possible, one or two biopsy specimens should be snap-frozen and stored.
- Perform laboratory tests to rule out alternate etiology (i.e., WBCs and stool calprotectin).

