Appendix Table 8 Management Guidelines for GI Events (Diarrhea/ Colitis)

GI Events (Diarrhea/Colitis)	Severity	Management
	Grade 1 diarrhea or colitis	
 • Continue therapy • Symptomatic treatment • Endoscopy is recommended if symptoms persist for greater than 7 days. • Close monitoring
	Grade 2 diarrhea or Grade 2 colitis	
 • Withhold atezolizumab • Symptomatic therapy • GI consultation recommended • If persists  5 days or recurs: Prednisone 60 mg/day or equivalent • Taper steroids over  1 month when symptoms improve to Grade 0 or 1 • Treatment may be resumed if the event improves to Grade 0 or 1 within 12 weeks and corticosteroids have been reduced to the equivalent of prednisone 10 mg PO daily or less.
	Grade 3 diarrhea or colitis	
 • Withhold atezolizumab • GI referral and confirmation biopsy • Treat with IV steroids (1-2 mg/kg/day methylprednisolone or equivalent) and convert to oral steroids (prednisone 60 mg/day or equivalent) after improvement • When improves to Grade 0 or 1, then taper steroids over \geq 1 month • Treatment may be resumed if the event improves to Grade 0 or 1 within 12 weeks and corticosteroids have been reduced to the equivalent of oral prednisone 10 mg daily or less.
	Grade 4 diarrhea or colitis	
 • Discontinue atezolizumab • GI referral and confirmation biopsy • Treat with IV steroids (1-2 mg/kg/day methylprednisolone or equivalent) and convert to oral steroids (prednisone 60 mg/day or equivalent) once improvement • When patient's diarrhea or colitis improves to Grade 0 or 1, then taper steroids over \geq 1 month • If not improving after 48h of initiating steroids or worsening, addition of an alternative immunosuppressive agent (e.g., mycophenolate or TNF-α antagonist) may be considered. • Contact medical monitor if atezolizumab is discontinued.

GI=gastrointestinal; PO=per oral; TNF- α =tumor necrosis factor alpha.

Endocrine Events

Thyroid disorders or adrenal insufficiency has been associated with the administration of atezolizumab.

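### Section 5.4.3 lets atezolizumab restart at Grade 0–1 where Appendix F requires a stop or sets limits, and no text makes Appendix F prevail on restart for non-DLT events; control-arm duration (8.2.3.2) and the overdose cut (9.4.1) also conflict with other protocol text

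*Protocol*

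**What the plan says.** *Restart.* Protocol Section 5.4.3 lists nine kinds of event for which atezolizumab is held, then states: "Atezolizumab treatment can be resumed in patients whose adverse reactions recover to Grade 0-1". The synopsis row on atezolizumab toxicities repeats this. Neither place limits restart by original grade, elapsed time or steroid dose, and neither names Appendix F. Section 5.4.3 adds "These reactions, along with any DLTs, will be reviewed by the DMC on a case-by-case basis", and says they may count as DLTs.

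Appendix F gives rules by event. For Grade 3 and 4 pneumonitis (Appendix Table 6): "Permanently discontinue atezolizumab". For Grade 2 pneumonitis: "Atezolizumab may be resumed if the event improves to Grade 0 or 1 within 12 weeks and corticosteroids have been reduced", the steroid limit being 10 mg of prednisone equivalent a day. For Grade 3 and 4 hepatic events (Table 7): "Discontinue therapy". For Grade 4 diarrhea or colitis (Table 8): "Discontinue atezolizumab".

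*Duration.* Section 8.2.3.2 item 6 gives control patients atezolizumab for 1 year from Day 0. The heading of that same section, Table 2 footnote l, the Figure 1 note and Sections 5.2 and 5.7 all give up to 2 years.

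*Overdose.* Section 9.4.1 defines an atezolizumab overdose as 1000 mg or more and describes that as five times the dose. Section 7.1.3.3 fixes the dose at 1200 mg, and Section 7.2.2 allows no change to it.

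**The concern.** Each conflict is between two pieces of current text, so a site can comply with one and breach the intent of the other.

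- **Restart** is the safety issue. A patient whose Grade 4 pneumonitis recovers to Grade 1 may be rechallenged under 5.4.3 and must not be under Appendix Table 6. Appendix Table 3 records four fatal pneumonitis reports with atezolizumab, though pneumonitis was seen mainly in lung cancer.
- **Duration** bears on the comparison between arms. If the 1-year clause were followed, controls would stop while the combination arm went on to 2 years. The arms would then differ in atezolizumab as well as CMB305 after month 12, which would confound the exploratory late PFS and OS comparisons.
- **Overdose** bears on reporting. Section 9.4.1 requires overdoses to be reported at once, whatever the outcome, yet the numeric cut lies below one planned infusion.

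**Working it through.** **1. Restart: 5.4.3 beside Appendix F**

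| 5.4.3 item | Appendix F stop rule that the 5.4.3 restart sentence lacks |
|---|---|
| Pneumonitis, Grade ≥2 | Table 6: stop at Grade 3–4; Grade 2 may restart within 12 weeks at ≤10 mg/day |
| Hepatic | Table 7: stop at Grade 3–4 |
| Diarrhea/colitis, Grade ≥2 | Table 8: stop at Grade 4; Grade 2–3 may restart within 12 weeks at ≤10 mg/day |
| Endocrine | Table 9: stop for symptomatic pan-hypopituitarism and Grade 3–4 events |
| Ocular, Grade ≥3 | Table 10: stop at Grade 3–4 |
| Dermatologic, Grade ≥3 | Table 13: stop if life-threatening (Grade 4) |
| Neuropathy, Grade ≥2 | Table 14: stop if life-threatening; stop for myasthenia gravis or Guillain-Barré at any grade |
| Hematologic | no table |
| Other organ toxicity, Grade ≥3 | no single table |

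So 7 of 9 items have a stop rule in Appendix F that 5.4.3 lacks. This counts items, not patients.

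Two details also differ. The 5.4.3 hepatic trigger is partly "Grade ≥ 3 asymptomatic hepatic toxicities that do not resolve to Grade ≤ 1 within 3 weeks of onset", whereas Table 7 stops at Grade 3–4 without waiting. And 5.4.3 excludes from its last item a "Grade 3 infusion reaction that resolves within 6 hours to Grade ≤ 1", while Section 7.4.4.1 and Table 11 bar further infusion after any Grade 3–4 reaction.

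The documents give no Grade 3–4 rates for pneumonitis, hepatic, endocrine or ocular events. For pneumonitis the any-grade single-agent rate in Appendix Table 3 is 1.4%, so 0.014 × 80 = 1.1 patients is a rough ceiling, if the single-agent rate applies here.

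**2. Control-arm duration**

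Infusions at 21-day spacing from Day 0 number floor(days/21) + 1.

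- 1 year: floor(365/21) + 1 = 17 + 1 = 18
- 2 years: floor(730/21) + 1 = 34 + 1 = 35

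If one cycle in three after Day 105 always takes the permitted extra week (70 days per three doses), the counts are 6 + 11 = 17 and 6 + 26 = 32.

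For the number of controls affected, take the plan's median PFS values of 3 and 5.2 months and assume exponential PFS:

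- 0.5^(12/3) = 6.25%, or 2.5 of 40
- 0.5^(12/5.2) = 20.2%, or 8.1 of 40

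This ignores toxicity stops and treatment beyond progression.

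**3. Overdose**

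The plan's figure does not reproduce: 5 × 1200 = 6000 mg, not 1000 mg. Read backwards, 1000/5 implies a 200 mg dose, which appears nowhere in the atezolizumab dosing text. One planned infusion is 1200/1000 = 1.2 times the cut.

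**The case against.** The strongest reply is that the protocol already leans to Appendix F. The synopsis (Safety Monitoring) and Section 7.2.2 make withholding as set out in Appendix F mandatory. Section 5.6 leads there through 7.2.2, and Section 7.4.4 applies the Appendix F guidance to related events. After a DLT, Sections 5.6 and 7.2.2 suspend treatment, and any further dosing is decided case by case in consultation with the DMC. Section 6.3 requires stopping for intolerable toxicity. The 5.4.3 sentence is permissive, so a site that follows Appendix F does not breach it. Items 2 and 3 look clerical.

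Most of this stands, and it rules out several stronger readings that a reader might infer:

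- *That the protocol gives no guidance on which text to use, or that someone reading only the synopsis would not be sent to Appendix F.* The synopsis sends that reader there in its Safety Monitoring row.
- *That rechallenge never needs prior DMC input.* It does for DLTs.
- *That the 6-hour exclusion authorizes re-infusion.* It only removes an event from one withholding item.
- *That controls will in fact stop at 1 year.* The weight of the text is for 2 years. The clause matches Booster Phase item 7 in 8.2.3.1 and was probably copied from it. The same section also gives controls LV305-related blood tests that Table 2 lacks.
- *That every infusion will be reported as an overdose.* The general definition in 9.4.1 also requires the dose to be excessive and medically important.

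The reply does not close the gap on restart. The mandatory sentences concern withholding. Section 7.2.2 itself treats skipping a dose and stopping as alternatives for higher-grade immune events. The DLT route is limited: Section 5.4.2 ties its general DLT definition to the first 42 days and to the combination, and does not immediately count atezolizumab-attributed events as DLTs except as noted in 5.4.3.

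**Conclusion.** The point holds in three limited parts.

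1. The restart sentence in 5.4.3 and the synopsis contradicts Appendix F. No text makes Appendix F prevail on restart or permanent stop for events not classed as DLTs. Other sections reduce the practical risk, and no event count can be given beyond the rough ceiling for pneumonitis.
2. Section 8.2.3.2 item 6 is wrong as printed. Followed literally, it allows at most 18 rather than 35 control infusions and makes atezolizumab duration unequal between arms after month 12. Under the stated exponential assumption, this would touch about 2.5 to 8.1 of 40 controls.
3. The overdose figure cannot serve as a threshold, because every planned infusion meets it.

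None of this changes the 6-month progression-free rate design, its sample size or its error rates. The duration conflict starts only after month 12. The corrections are worth making because one concerns rechallenge after severe toxicity and all are cheap.

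**What to change.** 1. In 5.4.3 and the synopsis copy, replace the restart sentence with: *Atezolizumab may be resumed only where, and under the conditions in which, Appendix F and Section 7.4.4.1 permit; these govern resumption and permanent discontinuation.* Appendix F has no hematologic table, so also state which restart rule applies to listed events it does not cover. Keep the hepatic item and the 6-hour infusion-reaction exclusion for DLT classification only, and say that they do not authorize further dosing. Deleting them would be tempting but goes too far. Sections 5.4.2 and 5.4.3 use this list to decide which atezolizumab-attributed events are DLTs. One DLT among the three run-in combination patients adds six randomized patients (Section 5.4.1), and DLTs also feed the one-third suspension rule (Section 5.5).
2. In 8.2.3.2 item 6, change the control-arm period from 1 year to 2 years from Day 0.
3. In 9.4.1, replace the cut with a threshold above 1200 mg set by the sponsor's medical team, with a multiplier that matches it (6000 mg if five times is intended).

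The cost is amendment wording and a site notice. With the DLT criteria left intact, no patients, visits or procedures are added.

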5.5 Study Stopping Rule

The preliminary safety of the individual components of CMB305 (LV305 and G305) have been studied in separate Phase 1 studies; however, the safety of the CMB305/atezolizumab combination will be investigated during the 6-12 patient Safety Run-in. The safety profile of CMB305 is discussed in the IB.⁶ Dosing will be suspended in this study if DLT is observed in one third or more patients on the combined regimen (assuming a minimum of 12 combined regimen patients were enrolled at that point and would represent the initial denominator), pending review and recommendation from the DMC.

The Sponsor may also choose to terminate this study at any time. Investigators will be notified if the study is placed on hold, completed, or closed.

5.6 Dosing Delays/Dose Modifications

There are no adjustments for dose delays for a given patient. Treatment delays of >14 days from the treatment plan for CMB305 components prior to Visit 12 are not permitted. If a patient experiences a DLT during the study, their treatment will be suspended. Further treatment of this patient with LV305, G305, or atezolizumab will be made on a case-by-case basis following evaluation of the risks/benefits by the Investigator and Medical Monitor in consultation with the DMC.

Dosing interruptions are permitted in the case of medical/surgical events or logistical reasons not related to study therapy (e.g., elective surgery, unrelated medical events, patient vacation, and/or holidays). Patients should resume study therapy within 3 weeks of the scheduled interruption, unless otherwise discussed with the Sponsor. The reason for the interruption should be documented in the patient's study record. Further details regarding dosing delays and modifications are provided in [Section 7.2.2](#).

5.7 Overall Study Duration and Follow-Up

The expected duration of patient participation on study treatment is 2.1 years. The study period will consist of Screening (study Day -30 to -1), Treatment Phase (study Days 0 to 84), Booster Phase (in the combined treatment arm) with continuation of G305 boosters (post Day 84 to 1 year [post Day 0] or until disease progression), Maintenance Phase with continuation of atezolizumab treatment (for the combined treatment arm, 1 year to 2 years [post Day 0] and, for the control arm, post Day 84 to 2 years [post Day 0], or until disease progression), and Survival Follow-up Phase (quarterly thereafter). The overall study duration will depend on speed of enrollment and time to the number of events.

Following completion of CMB305 dosing, patients will continue with imaging and clinical assessment every 6-9 weeks until disease progression, as defined by the RECIST v1.1 criteria modified to use irRC ([Section 6.3](#)). Patients or their physicians will then be contacted by the sites every 3 months by telephone to assess OS.

For patients receiving CMB305, blood will be collected to test for LV305 persistence at baseline and then at 6, 12, and 24 months following the first study treatment administration. Depending on the results from the 12-month sample, annual assessments may continue until 2 consecutive yearly samples show no evidence of LV305 persistence.

Patients with confirmed radiographic disease progression by irRC will be followed thereafter by the site every 3 months by contacting their primary physician by telephone as long as they are able to engage in follow-up until date of death recorded. Follow-up telephone contact will ascertain vital status, as well as possible occurrence of second malignancies and any SAE that might be possibly related to CMB305 treatment.

